## **5.0 Enrollment/Randomization**

This is a parallel study where participants will be assigned to either taking the study drug (lanadelumab) or taking the placebo (saline pre-filled syringes.) Patients will be randomly assigned to the treatment order using a permuted-block randomization algorithm. The study drug, lanadelumab, will be shipped from Takeda as pre-filled syringes along with matching placebo, also in prefilled syringes. The Vanderbilt Investigational Drug Services (IDS) will be responsible for the storage, preparation, dispensing, and labeling of the investigational agents. The Vanderbilt IDS will also maintain accurate drug storage and dispensing logs. Subjects will be randomized to receive a placebo or 300 mg of lanadelumab (Takeda Pharmaceutical, Cambridge, MA). Subjects randomized who do

not complete the whole protocol for any reason will be replaced, and their data will be analyzed separately. The half-life of lanadelumab is 14 days, and the time to reach maximum concentration is five days. For this reason, we will monitor blood pressure and the occurrence of DIH for three weeks after the administration of the second dose of the study drug.

[figure not shown]

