## 6.0 Study Procedures

### Study protocol

After obtaining consent, study subjects will undergo the following procedures.

**COVID-19 precautions prior to and during visits.** Pre-visit phone call – we will contact the patient before all of their study visits to ask a series of COVID-19-related screening questions. Depending on their answers, we will continue with the study visit or postpone for another time. The patient will be asked to wear a face covering during all portions of their study visits in which they are in the presence of hospital staff. We will also encourage frequent hand washing and/or provide alcohol-based hand sanitizer.

Subjects will participate in a randomized, parallel-group, double-blind, placebo-controlled study in which they will receive two doses of placebo or 300 mg of lanadelumab subcutaneously. Participants will continue their usual medications throughout the study. One week (Day -7) before the administration of the first dose of the study drug, we will conduct a study visit at the hemodialysis unit. During this visit, we will give the participants a physical activity monitor to be worn for at least 5 consecutive days and will obtain baseline blood samples. During a second study visit at the dialysis unit (Day -1), we would obtain a second baseline blood sample one to three days before the administration of the first dose of the study drug. In this visit, we will also measure

muscle oxygenation using near-infrared spectroscopy (NIRS). Patients will be then asked to come to the Vanderbilt Clinical Research Center (CRC) on a non-dialysis day. During this visit (Day 0), we will obtain a detailed history, perform a physical examination, administer a quality of life (QOL) questionnaire, obtain the dialysis recovery time, and evaluate body composition and physical performance. We will then administer the first dose of the study drug and monitor the appearance of any Type I (immediate) hypersensitivity reaction for two hours before discharging patients from the CRC. We will repeat the same protocol, as outlined for Day 0 and administer the second dose of the study drug two weeks later at the CRC (Day 14).

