The next two consecutive dialysis treatments after each drug administration (days 1 and 3, and days 15 and 17), we will conduct follow-up visits at the dialysis unit to collect information regarding symptoms after discharge from the CRC. During these visits, at the end of every hemodialysis session, we will also inquire, through a standardized questionnaire, about the presence of any symptoms associated with hypotension. This questionnaire will include symptoms such as cramps, dizziness, nausea, and will be scored according to the severity from 0 to 4 (none to severe). We will also collect blood samples at the dialysis unit for pharmacokinetics and special laboratory analysis. During the six-week length of the study, we will monitor the occurrence of DIH episodes and changes in blood pressure in every dialysis session. For this purpose, we will use the dialysis clinic blood pressure monitor logs. We will also conduct two additional visits at the dialysis units (Day 29 and 43) to draw blood, administer the symptomatology questionnaire, and measure blood flow with NIRS. In the final hemodialysis visit (day 43) we will also give the patients an activity monitor that will be collected after five consecutive days of continuous use. During this last visit, we will also administer the QOL questionnaire, obtain the dialysis recovery time, and perform body composition and physical performance tests (except for the six-minute walk test). Details of the study protocol can be found in Figure 5, Tables 1 and 2, and Appendix 1

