### ***b. Data analysis plan***

Standard graphing and screening techniques will be used to detect outliers and to ensure data accuracy. Distributions of the continuous outcomes will be assessed for normality. If normality is violated, proper data transformation will be applied, or non-parametric analysis methods will be considered. The primary endpoints are SBP and DBP. The secondary endpoints include heart rate, and the R-R interval (autonomic function), the time to recover after HD, symptoms associated with DIH, and the distance walked during the six-minute walk test.

Mixed effect models will be used to analyze the primary endpoint (blood pressure) with a random subject effect and with the treatment (lanadelumab vs placebo) and the time trend (measurements every 15 minutes) as fixed effects. The focus of this study will be the treatment effect and the time trend of the endpoints; however, mixed effect models also provide the flexibility of controlling for and evaluating covariates. However, we will be careful not to over-fitting the model due to the limited sample size.

Besides the above evaluation of the treatment effect and the time trend through the regression models, the direct treatment effect will also be estimated as within-subject mean difference along with their 95% confidence intervals. For the secondary endpoints, a paired t-test will be performed (lanadelumab vs placebo). If the normality of the data is violated, we will use non-parametric tests.

For binary endpoints (e.g., occurrence of hypotensive events), we will use the McNemar test to compare lanadelumab and placebo.

**Missing Data.** Based on our previous studies, we anticipate a drop-out rate of 10% or less. Subjects who drop out will be replaced. Specific inferences on effects of interest will be made by reporting a point estimate along with a 95% confidence interval and the p-value. Hypotheses will be tested at the level of  $\alpha=0.05$ . We will use SPSS (version 25.0, SPSS, Chicago, IL) and the open-source statistical package R (R Core Team, 2017) for analyses.

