## Appendix A Summary of study procedures

	+/-3 days						+/-4days				
	Day-7	Day -1	Day 0	Day 1	Day 3	Day 13	Day 14	Day 15	Day 17	Day 29	Day 43
CRC visit			X				X				
HD visit	X	X		X	X	X		X	X	X	X
Blood draw PK		X		X	X			X	X	X	X
Blood draw clinical labs	X				X	X			X	X	
Blood draw research labs		X		X				X			X
Serum pregnancy test			X				X				
Drug administration			X				X				
Medical history /PE			X								
QOL questionnaire/ recovery time			X				X				X
Symptoms questionnaire/ BP monitoring log				X	X			X	X	X	X
NIRS		X						X		X	X
Physical performance tests - Body composition***			X				X				X***
Collect dialyzer		X		X	X			X	X	X	X
activity monitor*	X*										X*

\* monitor ends after at least 5 days of consecutive use

\*\*It includes: physical performance tests (six-minute walk test, physical battery, and handgrip strength), bioelectrical impedance analysis, and MUAMC

\*\*\*Physical performance will only include handgrip strength

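### The six-minute walk endpoint can show only the effect 14 days after one dose, its planned paired test does not fit two parallel arms, and the Day 43 function-test list is contradictory.

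*Combined protocol and SAP*

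**What the plan says.** **Order of tests and dosing.** On Day 0, Section 6.0 (Study protocol) has staff "evaluate body composition and physical performance. We will then administer the first dose of the study drug". For Day 14 it says "We will repeat the same protocol, as outlined for Day 0 and administer the second dose of the study drug two weeks later". Appendix A marks physical performance tests on Days 0, 14 and 43, and drug administration on Days 0 and 14.

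**What the tests are.** Section 6.0 (Physical performance tests) lists the six-minute walk, a physical battery made up of gait speed and chair stand, and handgrip strength.

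**Day 43.** The Study protocol text says staff will "perform body composition and physical performance tests (except for the six-minute walk test". The Appendix A footnote attached to the Day 43 entry says "Physical performance will only include handgrip strength".

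**Analysis.** Section 10.0 b includes "the distance walked during the six-minute walk test" among the secondary endpoints and plans a paired t-test of lanadelumab against placebo for them. Section 10.0 a places secondary endpoints in the second week of treatment, but its own list does not include the walk. Sections 5.0 and 6.0 describe a parallel-group trial.

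**Pharmacokinetics.** Section 5.0 states: "The half-life of lanadelumab is 14 days, and the time to reach maximum concentration is five days".

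**The concern.** The trial gives two doses, so a reader will take a secondary endpoint to describe the two-dose course unless told otherwise. For the walk it cannot, and no section says so.

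The planned test adds a second difficulty. A paired comparison of treatments needs both treatments in the same person, and a parallel design does not provide that. An analyst would have to replace the method after the data are in, or pair Day 14 with Day 0 inside each arm, which does not compare the arms.

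The Day 43 conflict affects data collection. Staff following Section 6.0 would record gait speed and chair stand; staff following Appendix A would not. If both documents are in use, these tests could be present for some participants and absent for others, for reasons unrelated to the patients.

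**Working it through.** **1. When the walk is measured**

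| Visit | Walk | Doses received by then |
|---|---|---|
| Day 0 | yes, before dosing | 0 |
| Day 14 | yes, before dosing (Day 0 sequence repeated) | 1 |
| Day 43 | no, in both sources | 2 |

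There is one post-baseline value, at 14 − 0 = 14 days after dose 1, and none after dose 2. The result barely depends on the order within Day 14. Even if the walk followed the injection, it would fall on the same day as a dose whose stated time to maximum is five days.

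**2. Whether the test fits the design**

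A paired t-test needs a difference, lanadelumab minus placebo, within each participant. Each participant receives one of the two, so the number of such pairs is 0. The alternatives are:
- pairing a treated with an untreated participant, for which the plan describes no matching;
- pairing Day 14 with Day 0 within an arm, which gives change over time and not a treatment comparison.

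The only design calculation in the plan concerns blood pressure, but it points the same way. With SD 13.6, difference 13.7, two-sided 0.05 and 80% power, the two-sample normal formula gives n = 2 × (1.960 + 0.842)² × (13.6/13.7)² = 2 × 7.849 × 0.985 = 15.5, so 16 per arm. That is the stated figure. A true paired t-test with these inputs would need 10 pairs. So the stated figure is a two-group one, although the text calls the test paired.

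**3. Which tests are done on Day 43**

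| Test | Section 6.0, Study protocol | Appendix A footnote | Value after dose 2? |
|---|---|---|---|
| Six-minute walk | no | no | no |
| Gait speed | yes | no | unclear |
| Chair stand | yes | no | unclear |
| Handgrip | yes | yes | yes |

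The two sources agree on two tests and conflict on two.

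**4. Exposure at the visits (for the optional remark only)**

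From the documents: half-life 14 days, time to maximum 5 days, equal doses on Days 0 and 14. Assumed: linear one-compartment kinetics with first-order absorption.

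- Elimination rate: ke = ln 2 / 14 = 0.0495 per day.
- Absorption rate: ka solves ln(ka/ke)/(ka − ke) = 5, giving ka = 0.520 per day. Check: ln(10.50)/0.470 = 5.0.
- One dose: c(t) = [ka/(ka − ke)] × (e^(−ke·t) − e^(−ka·t)), with leading factor 1.105. Two doses: c(t) + c(t − 14).
- Peak of the sum: 1.222, at about Day 18.

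| Day | From dose 1 | From dose 2 | Sum | Share of peak |
|---|---|---|---|---|
| 14 | 0.552 | 0 | 0.552 | 45% |
| 29 | 0.263 | 0.525 | 0.788 | 65% |
| 43 | 0.131 | 0.263 | 0.394 | 32% |

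Appendix A shows a 4-day window whose columns are not clear in the extracted table. If it covers Day 43, the share runs from 39% (Day 39) to 26% (Day 47). With a time to maximum of 3 to 4 days instead of 5, the shares are 40–42% on Day 14, 57–60% on Day 29 and 28–30% on Day 43.

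**The case against.** The strongest defence is that Section 10.0 a puts secondary endpoints in the second week of treatment. Counted from Day 0 that is Days 7 to 14, so a Day 14 walk is inside the plan's own window. This stands: the Day 14 measurement is legitimate. It does not remove the need to say that the measurement reflects one dose.

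The omission of the walk on Day 43 also looks deliberate. Both sources make it, Day 43 is a dialysis-unit visit, and the walk needs a 30-meter corridor. So it should not be called an oversight.

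Gait speed and chair stand appear in neither list of secondary endpoints. That limits the consequence of the Day 43 conflict, but two incompatible collection instructions still need one answer.

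A reader might go further and infer that walking, quality of life and activity are all measured at exposures too low to be informative, so that a null result could not be interpreted. The documents do not support this:
- They give no exposure-response relation, so 45% or 32% of the peak is not shown to be ineffective. In the same model Day 14 is still 0.552/0.781 = 71% of the first-dose peak.
- The pharmacokinetic argument in Section 5.0 is made for blood pressure and DIH only: "we will monitor blood pressure and the occurrence of DIH for three weeks after the administration of the second dose of the study drug".
- In this model, mean exposure over Days 7 to 14, a window that Section 10.0 a also uses for the primary outcome, is about 53% of the two-dose peak. The plan does not require measurement at peak.
- KDQOL-SF and activity are collected but are not listed endpoints in Section 10.0.
- Function and quality of life may respond to benefit accumulated over weeks, which would favour a late assessment. The Day 43 activity recording ("In the final hemodialysis visit (day 43) we will also give the patients an activity monitor") is therefore a defensible choice.

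**Conclusion.** Three statements hold, and none needs a pharmacokinetic model:

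- The walk, a named secondary endpoint, has one post-baseline value, 14 days after one dose. It cannot describe the two-dose course.
- A paired t-test between arms cannot be carried out as a treatment comparison in this parallel design.
- Section 6.0 and Appendix A conflict on two of the four function tests on Day 43. That decides whether gait speed and chair stand have any value after dose 2.

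The walk finding rests on reading the Day 14 visit as following the Day 0 order, which is what Section 6.0 says. Walk timing and the Day 43 list do not touch the primary blood pressure endpoint. The documents give no SD or baseline correlation for walk distance, so the precision of the walk comparison cannot be sized.

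That the KDQOL-SF and activity schedules are wrong does not follow. Exposure of about 32% of peak on Day 43 (26% to 39% with a 4-day window) against about 65% on Day 29 depends on the assumed linear model, and its relevance depends on effect following concentration. It supports a suggestion only.

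**What to change.** 1. **Section 10.0 b.** Define the walk endpoint as distance on Day 14. Compare the arms with a linear model that has treatment and Day 0 distance as terms, and report the adjusted mean difference with its 95% confidence interval. Where the plan falls back on non-parametric methods, name one for independent groups.
2. **Same section.** State that the walk is measured after one dose and before the second, and that its conclusion is limited to that.
3. **Section 6.0 and Appendix A.** Reconcile the Study protocol text with the footnote so that a single Day 43 test list applies to every participant.
4. **Optional.** Consider giving the KDQOL-SF also at the existing Day 29 dialysis visit, keeping Day 43. When activity is recorded is a design preference; moving the recording would give up the late record.

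Items 1 to 3 change wording only and add no visit. The Day 0 walk is already collected. If the reconciled list includes gait speed and chair stand, staff need space and equipment for them on Day 43. Item 4 adds one questionnaire per participant.
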